6. SELECTION & RECRUITMENT OF PARTICIPANTS

Study Participants

Study participants will include n=190 adolescents, ages 12-17, with T1D and their caregivers from Cincinnati Children's Hospital Medical Center (CCHMC), the University of Florida (UF) and the University of Colorado Barbara Davis Center for Diabetes (BDC). Adolescents and caregivers will be recruited during routine diabetes clinic visits and will meet the following inclusion/exclusion criteria:

Inclusion Criteria

- T1D diagnosis >1 year
- Adolescents with T1D ages 12-17
- Elevations on the Barriers to Diabetes Adherence questionnaire (scores of ≥ 2 of 5 for the Stress/Burnout and/or Time Pressure/Planning subscales) based on their previous clinic visit scores
- Ability to read/speak English (all measures are in English)

Exclusion Criteria

- Diagnosis of significant developmental disorders (e.g., autism spectrum disorder, moderate/severe developmental or intellectual disability)
- Comorbid medical diagnoses (e.g., cystic fibrosis) with the exception of endocrine disorders (e.g., Celiac disease, thyroid)

Recruitment Procedures

Potential participants meeting eligibility criteria will be identified by a trained research assistant in collaboration with the members of the Diabetes teams at each site. Specifically, patients will be pre-screened based on their scheduled appointments for inclusion/exclusion criteria.

Elevations on the BDA is one of our inclusion criteria for study entry. At CCHMC and the University of Florida, BDA elevations will most often be identified by reviewing responses from the patient's clinic visit or through a screening process. For eligible participants who do not have a completed Barriers to Diabetes Adherence (BDA) measure, study coordinators may administer a screening BDA to determine further study eligibility, but only after informed consent/assent is obtained. If the participant does not have any elevations on the BDA, they will be deemed a screen-fail and will not participate in the Diabetes Journey intervention. If the participant completes the BDA at a later clinic visit and has elevations on the BDA that make them eligible for study participation, and study staff determine they still meet all other inclusion criteria, the participant may be re-consented for study participation at that time.

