stratum will be used and stratification will be based on baseline A1C (i.e., $\geq 9\%$ or $< 9\%$), site (i.e., CCHMC, the University of Colorado Barbara Davis Center or the University of Florida), and Barriers to Diabetes Adherence elevation type within the treatment arm (i.e., elevated on one or both of the subscales). The A1C criterion was selected because the average A1C in 13-17 year olds with T1D in the US is 9%, which will result in comparable sample sizes above and below 9%. In addition, although the American Diabetes Association recommends an A1C $< 7\%$, very few adolescents achieve this. Site was chosen as a stratification variable to ensure balance for any site-related differences. This randomization strategy will minimize imbalance of the number of participants across groups. The randomization list will be held by an individual independent of the study to reduce any potential biases. Participants will be notified of their randomization group within 3 business days of completion of baseline data and be provided with appropriate materials (e.g., log-in information or website information and links). Total treatment time is up to 12 weeks, which coincides with routine quarterly T1D clinic appointments. This also enables sufficient time for cancelled and/or rescheduled sessions that are likely to occur given adolescents' busy schedules.

Control Group (Enhanced Standard of Care)

Participants randomized to Enhanced Standard of Care will receive general education via the T1DToolkit website, as well as 4 Zoom sessions (e.g., Zoom for Healthcare; See Appendix C) with certified diabetes educators (CDEs) from either CCHMC or UF across 12-weeks. Notably, if technical difficulties arise, telephone sessions will be conducted and audio recorded. Content to address adherence barriers were modified and or newly developed for the Enhanced Standard of Care group via the T1DToolkit website. Depending on the participant's elevated score(s) on the Barriers to Diabetes Adherence scale, patients will receive information specifically addressing elevated scales of the BDA. Treatment fidelity will be assessed via audio recordings and completion of checklists, which will be reviewed weekly by [name] with the CDEs who deliver this intervention.

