All Diabetes Journey participants will first receive the mandatory Introduction and Problem-Solving Modules. Participants with elevations on only one subscale will then receive 4 additional modules based on their individual subscale elevations (5 modules total). If the participant is elevated on both Barriers to Diabetes Adherence subscales, they will receive all 8 modules. This will yield completion of 5 or 8 total modules and 5 or 8 HIPAA compliant video-sessions (e.g., Zoom for Healthcare; See Appendix C) with a therapist from CCHMC or UF. No therapists will be utilized from the University of Colorado Barbara Davis Center.

The primary foundational skill that will be taught is problem-solving, the first core module. As a part of Problem-Solving Module, an engaging and visually appealing video reviewing problem-solving skills will be viewed. The following approach to teach problem-solving skills will be used: 1) Define the problem (e.g., feeling stressed and cannot sleep resulting in high blood glucoses); 2) Teach the adolescent to generate several solutions (e.g., deep breathing before bed, listening to relaxing music, talking to a caregiver); 3) Evaluate the pros and cons of each potential solution; 4) Select one solution for implementation; and 5) Review detailed solution with specifics regarding who, when, where, and how the solution will be attempted. The therapist plays a critical role in helping apply problem-solving skills in daily life. Notably, if technical difficulties arise, telephone sessions will be conducted and audio recorded. If adolescents lack access to mobile devices, an iPad will be provided to the participant.

Session	Content	Diabetes Journey Modules
1	Introduction and Problem Solving	Ticket Booth and Pirates of Problem-Solving
	Stress and Burnout	
	Stress	Stressolator
	Diabetes Burnout	Burnout Bumper Cars
	Emotional Control	The Mood Swing
	Time Pressure and Planning	
	Planning	Planning Parachutes
	Working Memory	Memory Monorail
	Inhibition	The Inhibitor Roller Coaster
5 or 8	Wrap-Up	Closing Time

The images below illustrate the draft layout of Diabetes Journey and the modules that will be used. Treatment fidelity will be assessed via audio recordings of the sessions and completion of checklists, which will be reviewed weekly by the supervising licensed psychologist at each site or designee. Treatment sessions may be delivered by interventionists at CCHMC or

the University of Florida.

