Given recruitment challenges and the resulting changes to eligibility and randomization, we decided to focus on the overall *Diabetes Journey* versus Enhanced Standard of Care difference at our primary endpoint, instead of powering for treatment subgroup comparisons. Using the same effect size estimates and assumptions in the original power analyses, but assuming a 1:1 randomization to only two groups, we determined that reducing the sample size from $N = 256$ to $N = 190$ ensured $>80\%$ power to detect a follow-up group difference effect size of $\Delta d = 0.36$, resulting in final group sizes of $n = 110$ in *Diabetes Journey* and $n = 80$ in Enhanced Standard of Care.

Randomization

At baseline, all participants who met inclusion/exclusion criteria (e.g., elevations on the Stress/Burnout and/or Time Pressure/Planning subscales of the Barriers to Diabetes Adherence questionnaire) were randomized to either the control group (i.e., Enhanced Standard of Care) or treatment group (i.e., *Diabetes Journey*). We used stratified block randomization with two strata and blocks of size 2 or 4 chosen randomly within each stratum. Stratification was based on baseline HbA1c (i.e., $>9\%$ or $<9\%$), site (i.e., CCHMC or University of Florida/University of

Colorado's Barbara Davis Center for Diabetes), and Barriers to Diabetes Adherence elevation type within the treatment arm (i.e., elevated on one or both of the subscales). The HbA1c criterion was selected because the average HbA1c in 13-17 year olds with T1D in the US is 9%, which resulted in comparable sample sizes above and below 9%. In addition, although the American Diabetes Association recommends an HbA1c <7%, very few adolescents achieve this. Site was chosen to ensure balance for any site-related differences. The randomization list was held by an individual independent of the study to reduce any potential biases. Those who were randomized were notified of their randomization status after completion of the baseline questionnaires so intervention materials could be provided immediately.

Measures

Definitions and Derivations (numbers at the end of variable names represent timepoint: 0=baseline; 1=post-treatment, 2=follow-up1 and 3=follow-up2)

Barriers to Diabetes Adherence (BDA) (Mulvey et al., 2011)				
Subscale	Descriptor	Items	Range	Interpretation
bdastress	BDA Stress and Burnout Subscale	4	1-5	↑ scores ↑ stress and burnout

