An intent to treat approach will be undertaken for all analyses. We will examine the data for intervention group comparability using chi-square tests for categorical variables (e.g., biological sex, insurance status, technology use) and t-tests for continuous variables (e.g., age, T1D duration) prior to analysis of the primary outcomes. Should we observe intervention group

differences at baseline on any variables, these variables will be added to the outcome models as covariates.

Our primary hypothesis examines group differences at the 6-month follow-up (i.e., primary end point) given that we expect participants to have made the most significant gains from the intervention after implementing the acquired skills for some time. Two separate Analysis of Covariance models (one for each barrier subscale) will be used to test the primary hypothesis that the *Diabetes Journey* intervention group will demonstrate significantly lower barriers compared to the Enhanced Standard of Care group at 6-month follow-up, after controlling for baseline barriers. For secondary outcomes (i.e., HRQOL, T1D self-management behaviors, HbA1c), the same analytical approach will be used, with baseline values of the respective outcome included as a covariate. To evaluate the treatment effect on our primary and secondary outcomes across time, we will employ Generalized Estimating Equations (GEE), while controlling for baseline covariates.

Handling Missing Data

Missing data will be addressed using full information maximum likelihood (FIML) under the assumption of data missing at random (MAR) in the ANCOVA models. For the longitudinal GEE models, we will use multiple imputation to address missing data under the assumption that the data are Missing at Random (MAR). The imputation will use chained equations (mi impute chained) with relevant predictors to generate 100 imputed datasets.

Variables:

Outcome variables:

- Primary: BDA subscale scores for stress and time pressure (bdastress, bdatime)
- Secondary: alc, T1DAL subscales and total score (t1dalhandlingt1d, t1daltpeer, t1daltfamily, t1dalemotionr, t1daltotalr)
- **Group (independent variable):**
 - condition (0 = ESC, 1 = DJ)
- **Timepoints:**
 - time (post-treatment = 1, follow-up 1 = 2, follow-up 2 = 3)
- **Covariates:**
 - age (continuous)
 - sex (categorical, 0 = male, 1 = female)
 - insurance (insur, 0=public, 1=private)
 - time since dx (timedx, continuous)
 - use of technology (cgm yes = 1, cgm no = 0)

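### Each primary ANCOVA includes participants not elevated on the subscale tested and given none of its specific modules, and the power assumptions do not allow for a smaller effect in them

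*Protocol*

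**What the plan says.** - **Entry.** Protocol section 6 admits adolescents with "scores of ≥ 2 of 5 for the Stress/Burnout and/or Time Pressure/Planning subscales", based on scores from a previous clinic visit. A participant may therefore be elevated on one subscale only.
- **Treatment arm.** Protocol section 8: "All Diabetes Journey participants will first receive the mandatory Introduction and Problem-Solving Modules". After that, "Participants with elevations on only one subscale will then receive 4 additional modules based on their individual subscale elevations". Only those elevated on both subscales get all eight modules. The module table lists three modules specific to each subscale, plus the shared first session and a wrap-up.
- **Control arm.** Content is tailored too: "patients will receive information specifically addressing elevated scales of the BDA".
- **Primary analysis.** SAP, Primary Aim Analysis Plan: "Two separate Analysis of Covariance models (one for each barrier subscale) will be used to test the primary hypothesis", and "An intent to treat approach will be undertaken for all analyses". The models are not restricted to participants elevated on the tested subscale. Elevation type (one or both subscales) is a randomisation factor but is absent from the SAP's covariate list.
- **Power.** The SAP states more than 80% "power to detect a follow-up group difference effect size of" 0.36 (0.55 minus 0.19) at N = 190. It lists six assumptions, and none concerns participants who are not elevated on the subscale being tested.

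**The concern.** A participant elevated only on Stress/Burnout contributes fully to the Time Pressure/Planning model, yet neither arm was assigned content specific to that second barrier. A smaller group difference is plausible there, because the specific modules are missing and a low score on a 1–5 scale leaves little room to fall.

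The plan clearly expects such participants: it stratifies on elevation type and has a five-module track for them. If they are numerous, the all-randomised estimate averages the effect on a targeted barrier with a possibly smaller effect on an untargeted one. A null result could not then separate ineffective modules from averaging over people never assigned them.

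**Working it through.** **Inputs from the SAP:** group difference 0.36; R² = 0.30, so residual SD = √0.70 = 0.837; attrition 25%; arms 110 and 80.

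**Assumptions, because the documents give no value:** two-sided 5% test; p, the share elevated on the tested subscale; g, the effect in non-elevated participants as a fraction of the full effect; the same residual SD in everyone.

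**Step 1: reproduce the stated power.** SE = 0.837 × √(1/n₁ + 1/n₀), and power ≈ Φ(δ/SE − 1.96).

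- N = 256 (156/100), 25% loss, so 117/75: SE = 0.1238, 0.36/SE = 2.909, power 82.9%. This agrees with the SAP's figure of more than 80% at N = 256.
- N = 190 (110/80), no loss: SE = 0.1229, 0.36/SE = 2.928, power 83.4%.
- N = 190 with 25% loss, so 82.5/60: SE = 0.1420, 0.36/SE = 2.536, power 71.8%. A one-sided 5% test would give 81.4%.

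So at N = 190 the stated figure is reached with no information lost, or with a one-sided test, but not with a two-sided test and 25% loss. That gap exists before any dilution.

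**Step 2: allow for non-elevated participants.** δ = 0.36 × [p + (1 − p)g]. For example, p = 0.8 and g = 0.5 give 0.36 × 0.9 = 0.324. Power below is from the noncentral t (df = n − 3), with the normal approximation in brackets; the two differ by at most 0.6 points.

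| p | g | δ | No loss, 110/80 | 25% loss, 82.5/60 |
|---|---|---|---|---|
| 1.0 | – | 0.360 | 83.0% (83.4) | 71.2% (71.8) |
| 0.9 | 0 | 0.324 | 74.6% (75.0) | 62.0% (62.6) |
| 0.9 | 0.5 | 0.342 | 79.0% (79.4) | 66.7% (67.3) |
| 0.8 | 0 | 0.288 | 64.5% (64.9) | 52.2% (52.7) |
| 0.8 | 0.5 | 0.324 | 74.6% (75.0) | 62.0% (62.6) |

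With the protocol's 95/95 split, each figure is about one point higher. With no loss and g = 0, power at 110/80 falls below 80% once δ < 0.3444, that is p < 0.3444/0.36 = 95.7% (normal approximation).

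**Step 3: what p means.** Everyone is elevated on at least one subscale, so the average p over the two subscales is (1 + share elevated on both)/2. Thus p = 0.9 corresponds to 80% elevated on both, and p = 0.8 to 60%.

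**Step 4: all-randomised against elevated-only.** The signal is proportional to [p + (1 − p)g]√N for everyone and to √(pN) for those elevated. They are equal at g = √p/(1 + √p): 0.436, 0.456 and 0.472 for p = 0.6, 0.7 and 0.8. Above about 44–47% spill-over the all-randomised test has more power. With 25% loss and p = 0.8, the elevated-only comparison has 61%, against 52% (g = 0) or 62% (g = 0.5) for everyone.

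**The case against.** A reader might infer that 0.36 is diluted and that the power claim fails for that reason. The documents do not support this.

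- **Source of 0.36.** The 0.55 is an executive-function composite effect from an epilepsy study. The 0.19 comes from routine-care patients not described as selected for elevation. The difference is assumed for the whole arm comparison, so multiplying it by p is a model, not something the plan states.
- **Unknown split.** The cut-off is only 2 on a 1–5 scale. If nearly everyone is elevated on both subscales, the loss is small.
- **Shared content.** All treated participants get problem-solving, which the protocol calls the primary foundational skill, so zero spill-over is a worst case.
- **Separate shortfall.** With 25% loss, the fall to 71% precedes any dilution and should not be credited to it.
- **Variance.** If non-elevated participants vary less, equal residual SD overstates the loss. Halving their SD, as an assumption, gives about 59% instead of 52% at p = 0.8 with 25% loss and no spill-over.

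A reader might also infer that non-elevated participants start below 2. Eligibility may rest on an earlier clinic score, and screening and baseline questionnaires are listed separately, so the re-measured baseline need not be below 2.

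Finally, the all-randomised effect of a tailored programme is a legitimate intention-to-treat target, and the SAP says it chose the overall comparison over powering for treatment subgroups. That stands as a reason to keep the primary test. It does not explain why the power assumptions ignore non-elevated participants or why elevation is absent from the models.

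**Conclusion.** The mismatch is documented. Subscale-specific content in both arms follows elevation, while each primary model pools everyone without a term for it, and the power calculation makes no allowance. Whether this costs much cannot be determined from the documents.

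If 10–20% of participants are not elevated on the tested subscale, power with no loss drops from 83% to 75% or about 65% with no spill-over, or to 79% or 75% with half the effect. With 25% attrition, the corresponding drop is from 71% to 62% or 52%, or to 67% or 62%. These figures rest on a two-sided 5% test, R² of 0.30, arms of 110 and 80, and equal residual variance.

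The point does not show that the primary test is invalid, and it does not justify replacing it with an elevated-only test. It is worth acting on because the plan as written cannot show whether the tailored modules reduce the barrier they target.

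**What to change.** 1. Keep the all-randomised ANCOVA for each subscale as the primary test.
2. Add to each model an indicator for elevation on that subscale, defined by the pre-randomisation BDA score used to assign modules. State which score that is, since screening and baseline may differ. The one-or-both stratum cannot serve, because it does not say which subscale is elevated.
3. In a labelled supplementary model, add the interaction of this indicator with condition. Report the effect among those elevated beside the all-randomised effect, and mark it post hoc if outcomes have been seen. The SAP is dated November 2024 and describes conduct in the past tense, so this must be stated. Because the indicator is fixed before randomisation, the comparison remains randomised.
4. Give the observed share elevated on each subscale, and restate power over a range of assumed effects in non-elevated participants instead of as p × 0.36 alone.

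The cost is SAP wording, one covariate and one supplementary model per subscale. The targeted estimate uses fewer participants, and it has less power than the all-randomised test if spill-over exceeds about 44–47% of the full effect (p from 0.6 to 0.8). Restated power cannot change enrolment, but it would inform how a null result is read.

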8.1 Data collection procedures and measures

Participants will complete a demographic questionnaire that provides general information about the child's age, history of T1D, and family information. Both adolescents and caregivers will complete questionnaires. All participants will have the same baseline, post-treatment (3-months from baseline) and follow-up study visits (6 months from baseline), which includes questionnaires, diabetes device downloads, and health outcomes through medical chart reviews. In light of COVID-19, the COVID-19 Exposure and Family Impact Survey (CEFIS) will be administered to adolescents and caregivers to determine the impact of COVID-19 on their functioning (see Appendices J and K). The medical chart review will include key patient medical characteristics (e.g., insulin regimen type, A1C, PROs collected during routine clinical care)

Sources of data for the current study will include: 1) adherence data downloaded from blood glucose meters, continuous glucose monitors, insulin pumps, and hybrid closed loop systems; 2) REDCap web-based questionnaires completed by adolescents and caregivers assessing demographics, barriers to T1D adherence, health-related quality of life, depressive symptoms, T1D distress, executive functioning, family conflict, and feasibility/acceptability of the Diabetes Journey intervention; and 3) mail, electronic-mail, and telephone contact with participants to coordinate study visits and maintain study retention (See Appendices D, F, and E for relevant materials). T1D devices will be downloaded to industry standard HIPAA compliant software and cloud-based programs, which is diabetes standard of care.

Construct Measured	Respondent	Stages and Time points			
	C= Caregiver; Y=Youth M= Med Chart Review D= Doctor/ Clinician	Screening (may apply)	Baseline	Post Treatment (3-month post- txt)	Follow-up 1 (6- months post-txt)
ORDER OF MEASURES (As applicable)					
Background Questionnaires	C		X		
Diabetes-Related Executive Functioning Scale (DREFS)	Y/C		X	X	X
Diabetes Family Conflict Scale (DFCS)	Y/C		X	X	X
Barriers to Diabetes Adherence: Stress/Burnout and Time Pressure/Planning subscales (BDA)	Y	X	X	X	X
Type 1 Diabetes and Life (T1DAL)	Y		X	X	X
Problem Area in Diabetes- Teen Version (PAID-T)	Y		X	X	X
Patient Health Questionnaire-8 (PHQ-8)	Y		X	X	X
University of Virginia- Low Blood Sugar Survey	Y		X	X	X
ASWS	Y		X	X	X
Pittsburg (PSQI)	Y		X	X	X
COVID-19 Exposure and Family Impact Surveys (CEFIS)	Y/C		X	X	X
Satisfaction and Acceptability Questionnaire	Y/C			X	X
Device Downloads	Y		X	X	X
Fingerstick Blood Sample	D		X	X	X
Medical Record/Patient Record	D		X	X	X

8.2 Sample Size Considerations and Power Analysis:

Sample size for this study is based on our preliminary work with this intervention in epilepsy (i.e., Epilepsy Journey), which found moderate to large effect sizes from baseline to 6-month follow-up, ranging from $d = 0.55$ to $d = 0.93$ for the Global Executive Composite Score, the composite measure of the Behavior Rating Inventory of Executive Function, which represented our barriers outcome of interest. Additionally, preliminary data on our primary outcomes collected at CCHMC from 2016-2017 (i.e., Stress/Burnout and Time Pressure/Planning subscales) show that our patients improve slightly over one year with Enhanced Standard of Care, corresponding to an effect size of $d = 0.19$. A Monte Carlo simulation in Mplus with $n = 5000$ replications was conducted assuming: 1) proper handling of missing data; 2) 25% attrition; 3) standardization of all analysis variables; 4) at least 30% of the error variance in our primary outcome ($R^2 = 0.30$) being explained by baseline barriers scores and covariates; 5) we will observe the smallest effect size from our preliminary work in the treatment group (i.e., $d = 0.55$); and 6) we will observe a small improvement in our control group ($d = 0.19$). **Recent interim analyses and meetings with our NIH program officer have yielded a change in our study design from a fully powered RCT to detect subgroup differences to a pilot RCT focused on feasibility, acceptability, satisfaction and preliminary efficacy differences between the control and treatment groups. These new analyses indicate the need for a total sample size of $n=190$ ($n=95$ in the control group and $n=95$ in the treatment group).**

